6.1 Final Analysis

All final, planned analyses identified in the Clinical Trial Protocol and in this IAP will be performed only after the last subject has completed the treatment phase of the trial with all trial data in-house, all data queries resolved, and the database locked.

A data review meeting will be held prior to database lock. In addition, no database can be locked until this IAP has been approved.

7 Changes to the Planned Analyses in the Clinical Trial Protocol

The following changes were made in this IAP.

- Due to management decision, Part B from the protocol will not be further pursued. Therefore only Part A from the protocol is covered in this IAP.
- Analysis of exploratory endpoints from the protocol will not be performed.
- Listings will be presented based on the same analysis population as used in corresponding tables, which deviates from the requirement from the protocol: "listings will include all subjects who were enrolled, regardless of whether or not they received study treatment."
- Analysis of PK will not be performed, concentrations of VX-984 and PLD will only be listed by subject and nominal time.
- The definition of Full Analysis Set (FAS) from the protocol, to be used for efficacy analyses, is not used in this IAP. The updated version of FAS is defined in Section 8.2.

Definition of FAS per protocol: The FAS is defined as all subjects who received at least 1 cycle of study drug and have a baseline scan.

8 Protocol Deviations and Analysis Sets

8.1 Definition of Protocol Deviations

Protocol deviations will be collected by site monitoring and included in clinical trial management system log, no analysis planned.

8.2 Definition of Analysis Sets

Screening Analysis Set (SCR)

The SCR includes all subjects who provided informed consent.

Safety Analysis Set (SAF)

The SAF will include all enrolled subjects who received at least 1 dose of study treatment. Analyses performed on the SAF will consider subjects as treated.

Dose-Limiting Toxicity Evaluable Set (DLT)

The DLT will include all subjects in the SAF who either meet the minimum exposure criterion and have sufficient safety evaluations (as determined by the Investigators and sponsor) or have had a DLT during Cycle 1.

Subjects who do not have a DLT during Cycle 1 will be excluded from the DLT Evaluable Set if the subject does not satisfy either of the following criteria:

Minimum exposure criterion

A subject is considered to have met the minimum exposure criterion at a dose level if the subject received PLD on Day 1, and 3 doses of VX-984 within 5 days with the first dose of VX-984 on Day 2.

Completion of Cycle 1

A subject is considered to have sufficient safety evaluations if the subject has been observed through the end of Cycle 1, which is defined as up to 28 days after the start of study treatment from Cycle 1.

Subjects who have been replaced by Safety Monitoring Committee decision will also be excluded from this analysis set.

Full Analysis Set (FAS)

The FAS will include all enrolled subjects who received at least 1 dose of study treatment.

As the FAS is identical to the SAF, the term FAS/SAF will be used to reflect that those analysis sets contain the same subjects.

Pharmacokinetic Analysis Set (PAS)

The PAS will include of all subjects who receive at least 1 dose of VX-984 or PLD and provide at least one measurable post-dose concentration of VX-984 or one measurable post-dose concentration of PLD. Subjects will be analyzed according to the actual treatment they received. All PK listings will be based on this analysis set.

Use of analysis sets is described in Table 2.

Table 2 Summary of Analysis and Associated Analysis Set

Analyses	SCR	FAS/SAF	DLT	PAS
Dispositions and deaths	✓			
Baseline Assessments		✓		
Past and Concomitant Therapies		✓		
Compliance and Exposure		✓		
Efficacy		✓		
Safety: MTD (Primary endpoint)			✓	
Safety and Tolerability		✓		
PK				✓

9 General Specifications for Data Analyses

Unless otherwise indicated, summary tables will be presented by dose group and overall based on the analysis set of interest; listings will be presented using the same analysis sets as corresponding tables.

Data handling after cut-off date:

Data after cut-off do not undergo the cleaning process. The only exceptions are the date of death and the date last known to be alive, per the source data from the "Long-Term Follow-Up" case report form (CRF) page.

Data other than the date of death and the date last known to be alive obtained after the cut-off will not be displayed in any listings or used for summary statistics, e.g. laboratory values of samples taken after data cut-off, AEs with onset date after data cut-off, etc. will not be included in any analysis or listing.

Pooling of centers:

Because of the high number of participating centers and the anticipated small number of subjects enrolled in each center, data will be pooled across centers.

Presentation of continuous and qualitative variables:

Continuous variables will be summarized using descriptive statistics, i.e.

- Number of subjects, number of subjects with non-missing values (n)
- Arithmetic mean (Mean), standard deviation (StDev)
- Median, 25th Percentile 75th Percentile (Q1-Q3)
- Minimum (Min), maximum (Max)

If there are missing values, the number of subject counts and percentage should be indicated by a 0 (0.0).

Missing statistics, e.g. when they cannot be calculated, should be presented as "nd". For example, if n=1, the standard deviation cannot be computed and should be presented as "nd".

Qualitative variables will be summarized by counts and percentages.

Unless otherwise stated the calculation of proportions will be based on the number of subjects in the analysis set of interest. Therefore counts of missing observations will be included in the denominator and presented as a separate category.

In case the analysis refers only to certain visits, percentages will be based on the number of subjects still present in the trial at that visit, unless otherwise specified.

Presentation of PK Concentration Data

VX-984 and PLD concentration data will only be listed.

Presentation of PK Data

No PK parameter data will presented.

Definition of treatment day:

Treatment day is defined relative to the start of study treatment (either VX-984 or PLD) from Cycle 1.

Treatment Day 1 is defined as the day of the first administration of study treatment from Cycle 1. The day before is defined as Treatment Day -1 (no Treatment Day 0 is defined). Per protocol, the day of first administration of study treatment in Lead-in Period is Treatment Day -14.

Definition of baseline:

Baseline is defined as the last non-missing measurement prior to the first administration of study treatment (either VX-984 or PLD, whatever is earlier), including the Lead-in Period if available.

Definition of duration:

Duration will be calculated by the difference of start and stop date + 1 (e.g. survival time (days) = date of death – date of randomization + 1) (if not otherwise specified).

The time since an event (e.g. time since first diagnosis) will be calculated as reference date minus date of event.

Unscheduled visits:

Data collected at unscheduled visits will be included and analyzed for both safety and efficacy analyses in the same fashion as the data collected at scheduled visits except where otherwise noted. Assessments from unscheduled visits will be used for the derivation of baseline values and worst on-treatment values. However, descriptive statistics by nominal visit or time point for safety endpoints such as laboratory measurements, ECGs and vital signs will include only data from scheduled visits per protocol.

Conversion factors:

The following conversion factors will be used to convert days into months or years: 1 month = 30.4375 days, 1 year = 365.25 days.

Handling of missing data:

Unless otherwise specified, missing data will not be replaced.

In all subject data listings imputed values will be presented. In all listings imputed information will be flagged.

Missing statistics, e.g. when they cannot be calculated, should be presented as "nd". For example, if n=1, the measure of variability (StdDev) cannot be computed and should be presented as "nd".

SAS version:

If not stated otherwise, analyses will be performed using SAS® Software version 9.4 or higher.

10 Trial Subjects

The subsections in this section include specifications for reporting subject disposition and treatment/trial discontinuations.

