12.3 Concurrent Procedures

Analysis Set: FAS/SAF

Concurrent procedures, which were undertaken any time during the on-treatment period, will be listed according to the CRF page "Non-Pharmacological Treatment or Procedures".

In case the date values will not allow to unequivocally allocating a procedure to concurrent procedure, the procedure will be considered as concurrent procedure.

A listing of concurrent procedures will be created with the relevant information collected on the corresponding CRF page, including flags for procedures that took place prior to, on or after the date of first dose of study treatment (VX-984 or PLD), or after 30 days of the last dose of study treatment (VX-984 or PLD).

13 Treatment Compliance and Exposure

Analysis Set: FAS/SAF

All dosing calculations and summaries will be based on "Study Drug Administration: 984" and "Study Drug Administration: PLD" CRF pages.

- VX-984 is taken by consumption of dosing powder once daily (QD) on Days -14 to -12 as a single agent during a 14-day Lead-in Period, and Days 2 to 4 in a 28-day treatment cycle.
- PLD is administered by infusion to be taken on Day 1 in a 28-day treatment cycle.

Unless specified otherwise, Treatment Period refers to the dosing period that started from Cycle 1 Day 1 (Treatment Day 1); and Lead-in Period refers to the dosing period prior to Treatment Day1, (See the definition of Treatment Day in Section 9).

Total number of infusions of PLD

Total number of infusions is calculated as the sum of the actual number of infusions that a subject received across cycles. The actual number of infusions will be counted directly based on the infusions reported from the CRF, regardless of infusion delays, interruptions, or any other types of deviations from the protocol required schedules. An infusion is regarded to be administered, if either the actual dose received is > 0 mg or the duration of the infusion is > 0 minutes.

• PLD during the Treatment Period: per protocol a subject will receive 1 infusion in a 28-day treatment cycle.

Total number of administrations of VX-984

Total number of administrations is calculated as the sum of the actual number of administrations that a subject received during a period. The actual number of administrations will be counted directly based on the administrations reported from the CRF. A dose is regarded to be administered if the actual dose received is > 0 mg.

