15.1 MTD (Primary Endpoint)

Analysis Set: DLT

The maximum tolerated dose (MTD) is defined as the highest dose combination for a given schedule that causes DLTs in no more than 33.3% of subjects by the end of Cycle 1. The DLT information will be based on "Adverse Events" CRF page with "Dose limiting toxicity?" = Yes.

The end of Cycle 1 is defined as 28 days after the start of study treatment from Cycle 1 Treatment Day 1.

A summary table of DLTs during the first cycle of study treatment, including the Lead-in Period, will be provided by dose group and overall with:

- Number of subjects with no DLT
- Number of subjects with one or more DLTs

The listing of DLTs will also be provided.

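### The SAP's DLT Evaluable Set can drop subjects with a Lead-in DLT, although the DLT table run on it is meant to count Lead-in DLTs

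*SAP*

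**What the plan says.** **SAP Section 8.2.** Subjects in the Safety Analysis Set enter the DLT Evaluable Set by one of two routes, exposure with follow-up or an event: they have to reach the required exposure and "have sufficient safety evaluations (as determined by the Investigators and sponsor) or have had a DLT during Cycle 1". The exclusion rule uses the same period: "Subjects who do not have a DLT during Cycle 1 will be excluded from the DLT Evaluable Set if the subject does not satisfy either". Two criteria are then listed: minimum exposure (PLD on Day 1 and three VX-984 doses within 5 days, starting on Day 2) and observation to the end of Cycle 1. A further sentence adds: "Subjects who have been replaced by Safety Monitoring Committee decision will also be excluded from this analysis set".

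**SAP Sections 9 and 13, timing.** "Treatment Day 1 is defined as the day of the first administration of study treatment from Cycle 1". Under the same definition, "the day of first administration of study treatment in Lead-in Period is Treatment Day -14". Section 13 states that "Lead-in Period refers to the dosing period prior to Treatment Day1". Section 15.1 ends Cycle 1 at 28 days after Treatment Day 1.

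**SAP Section 15.1, run on the DLT set.** "A summary table of DLTs during the first cycle of study treatment, including the Lead-in Period, will be provided by dose group and overall". The section then promises a companion output: "The listing of DLTs will also be provided".

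**Protocol.** Section 12.2 defines the same set but expressly counts the Lead-in Period with Cycle 1 for the event route. The synopsis and Section 8.1.2.1.2 likewise treat a Lead-in DLT as making a subject evaluable for dose determination. Section 8.1.2.1.7 mentions only Cycle 1. Section 12.3.5 bases the DLT summary on the DLT Evaluable Set.

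**The concern.** The SAP says in Section 4 that it is based on protocol Section 12. Its Section 7 declares a changed Full Analysis Set but nothing for the DLT set. Yet the reference to the Lead-in has gone from the event route, and the exclusion sentence does not restore it.

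The subjects at risk of being lost are those in whom a DLT on VX-984 alone stops or disturbs Cycle 1. They would leave both the numerator and the denominator of the DLT table, so the tabulated rate would be too low. The error runs in one direction only, and with cohorts of 3 to 6 subjects a single loss is visible in the rate.

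**Working it through.** The documents give no figure for this point, so the check compares definitions and then works through the arithmetic of one lost subject.

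**Step 1. Does Cycle 1 in the SAP include the Lead-in?** Treatment Day 1 is the first Cycle 1 dose, the Lead-in starts on Day -14, and Cycle 1 ends 28 days after Treatment Day 1. On these definitions a Lead-in DLT does not fall in Cycle 1.

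**Step 2. Apply both definitions to a subject with a Lead-in DLT and no further DLT in Cycle 1.**

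| What follows the Lead-in DLT | Protocol 12.2 | SAP 8.2 as written |
|---|---|---|
| Cycle 1 never starts | In the set, by event | Out: no Cycle 1 DLT, and both criteria fail |
| PLD given, one VX-984 dose missed, observed to end of Cycle 1 | In the set, by event | Out under the inclusion sentence, which needs both criteria; the exclusion sentence is ambiguous |
| Full exposure and full observation | In the set | In the set |

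The first row is lost on any reading of the exclusion sentence. The second depends on whether failing one criterion is enough. The inclusion sentence says that it is.

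**Step 3. Compare with the table.** SAP 15.1 sets the event window to include the Lead-in, but the analysis set decides which subjects are counted. A table meant to show Lead-in DLTs is therefore run on a set that can leave out the subjects who had them.

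**Step 4. Size.** Let a dose group have x DLT subjects among n. Dropping one DLT subject changes x/n to (x − 1)/(n − 1). The fall is

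x/n − (x − 1)/(n − 1) = (n − x) / [n(n − 1)],

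which is zero only when every subject in the group has a DLT. The counts below are illustrative assumptions.

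| Case | Protocol 12.2 | SAP 8.2 | Fall in percentage points |
|---|---|---|---|
| No replacement, n = 3, x = 1 | 1/3 = 33.3% | 0/2 = 0% | 2/(3×2) = 33.3 |
| No replacement, n = 6, x = 2 | 2/6 = 33.3% | 1/5 = 20.0% | 4/(6×5) = 13.3 |
| One DLT-free replacement, n = 4, x = 1 | 1/4 = 25.0% | 0/3 = 0% | 3/(4×3) = 25.0 |
| One DLT-free replacement, n = 7, x = 2 | 2/7 = 28.6% | 1/6 = 16.7% | 5/(7×6) = 11.9 |

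The replacement rows apply only if protocol 8.1.2.1.7 governs. Read literally, that section requires replacement of a subject with a Lead-in DLT and incomplete Cycle 1 dosing. Protocol Section 9.6 limits replacement to withdrawals for reasons other than DLT. The two sections conflict for such a subject.

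**Step 5. Where the event would still appear.** The listing of all adverse events (SAP 15.2.1) carries a DLT flag, printed there as DTL. SAP 10.2 lists subjects excluded from the DLT set with the reason. The on-treatment period in SAP Section 15 includes the Lead-in, so the event also enters the treatment-emergent tables, though not labelled as a DLT. The DLT listing would share the omission if it follows the table's set, as SAP Section 9 provides.

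**The case against.** The strongest reply is that this is a dropped phrase and not a chosen narrowing. SAP 15.1 names the Lead-in, the SAP is built on protocol Section 12, and no change to the set is declared. Protocol 12.2 itself uses the short form later in the same definition, so the SAP's exclusion sentence alone is weak evidence of a second narrowing.

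That is probably the right account of how the text arose. It does not repair the text. In the protocol the short form follows a definition that includes the Lead-in; in the SAP's set definition nothing precedes it, and the SAP's own day count points the other way.

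It is also fair that the effect needs several things together: a DLT on VX-984 alone, failed exposure or observation as a result, no DLT in Cycle 1 itself, and programming that follows Section 8.2 to the letter. Protocol 8.1.3 makes discontinuation after a DLT discretionary, so failed exposure is not automatic. The loss could be noticed through the listings in Step 5 or at the data review meeting before database lock (SAP 6.1). These points limit the likelihood and make the error detectable, but they do not correct the planned count.

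Two further points stand as limits. Only the subject who never starts Cycle 1 is lost on every reading. And no passage says that a subject with a DLT would be replaced by Safety Monitoring Committee decision, so that route is a possibility to close and not a demonstrated loss.

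**Conclusion.** The concern holds. SAP 8.2 as written is narrower than protocol 12.2, does not declare the difference, and does not match the table in SAP 15.1 that depends on it. A subject with a Lead-in DLT who never starts Cycle 1 is excluded on any reading.

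The size is conditional. The documents do not say how often such a DLT would occur, and with none the effect is zero. With one, the tabulated rate falls by 33.3 points in a group of three with one DLT, or 13.3 points in a group of six with two, assuming no replacement.

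The protocol's own DLT set and its Bayesian MTD estimate (Sections 8.1.2.1.5, 12.3.3.1 and 12.3.3.3) are not affected. What is affected is the reported DLT incidence in the SAP and, if it follows the same set, the DLT listing. It should be fixed because the endpoint is primary and the correction is small.

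**What to change.** - In both sentences of SAP 8.2, extend the qualifying period so that a DLT in the Lead-in Period counts as well as one in Cycle 1, matching protocol 12.2.
- State that a subject with no DLT in either period is excluded if at least one of the two criteria is unmet.
- State that the exclusion of subjects replaced by Safety Monitoring Committee decision does not apply to a subject with a DLT.
- Reconcile protocol 8.1.2.1.7 with Sections 8.1.2.1.2, 9.6 and 12.2. They differ on Lead-in DLTs and on replacement. Section 8.1.2.1.7 also omits the observation to the end of Cycle 1 that Section 12.2 requires.
- If the narrower set is intended, declare it with a reason in SAP Section 7 and change the SAP 15.1 table description to match.

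The cost is a phrase in two SAP sentences, a short clarification beside them, and a brief protocol clarification. No new data or analyses are needed.

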# 8.1.2.1.7 Subject Evaluability

All subjects who meet the eligibility criteria and receive at least 1 dose of VX-984 will be evaluable for safety.

In order for subjects to be evaluable for dose escalation decisions:

- Subject must receive PLD on Day 1 and receive all 3 doses of VX-984 within 5 days (Days 2 to 6) with the first dose of VX-984 on Day 2; or
- The subject must have had a DLT during Cycle 1.

Subjects who do not fulfill at least 1 of the 2 above criteria will not be evaluable for dose escalation decisions and will be replaced.

In the event of a Grade 3 or higher elevation in ALT or AST, follow-up laboratory assessments should be performed every 48 to 72 hours until reduced to Grade 2 or lower.

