# 12.2 Analysis Sets

#### For Part A:

• The DLT Evaluable Set is defined as all subjects in the Safety Set of Part A who either meet the minimum exposure criterion and have sufficient safety evaluations (as determined by the Investigators and sponsor), or have had a DLT during Cycle 1 (including the Lead-in Period)

A subject is considered to have met the minimum exposure criterion at a dose level if the subject received PLD on Day 1 and 3 doses of VX 984 within 5 days with the first dose of VX-984 on Day 2. Subjects who do not have a DLT during Cycle 1 are considered to have sufficient safety evaluations if they have been observed through the end of Cycle 1 following the administration of PLD and VX-984, and are considered by both the sponsor and Investigators to have enough safety data to conclude that a DLT did not occur

- The Safety Set is defined as all subjects who received at least 1 dose of study drug. The Safety Set will be used for safety analyses
- The Full Analysis Set is defined as all subjects who received at least 1 cycle of study drug and have a baseline scan. The Full Analysis Set will be used for efficacy analyses.

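### SAP 8.2 defines the DLT Evaluable Set by two conflicting rules, and departs from the protocol on replaced subjects and Lead-in DLTs without declaring it

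*SAP*

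**What the plan says.** Protocol 12.2 (Part A) builds the DLT Evaluable Set from Safety Set subjects "who either meet the minimum exposure criterion and have sufficient safety evaluations (as determined by the Investigators and sponsor"). A second limb adds those who qualify through toxicity alone, and it reaches back before Cycle 1: "or have had a DLT during Cycle 1 (including the Lead-in Period"). For a subject without a DLT, both parts of the first limb are needed. Sufficiency means that the subject was observed to the end of Cycle 1 and that sponsor and Investigators agree the data are adequate.

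SAP 8.2 opens with nearly the same rule: subjects who "either meet the minimum exposure criterion and have sufficient safety evaluations (as determined by the Investigators and sponsor"), or who had a DLT during Cycle 1. The mention of the Lead-in Period is gone.

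The SAP then adds two exclusion rules:

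- A subject with no Cycle 1 DLT is excluded "if the subject does not satisfy either of the following criteria". The criteria that follow are minimum exposure, met "if the subject received PLD on Day 1, and 3 doses of VX-984 within 5 days with the first dose of VX-984 on Day 2", and observation through the end of Cycle 1.
- "Subjects who have been replaced by Safety Monitoring Committee decision will also be excluded from this analysis set".

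SAP Table 2 assigns the MTD, a primary endpoint, to this set. SAP 15.1 defines the MTD by a DLT proportion of no more than 33.3% and plans a table of subjects with and without DLTs, Lead-in Period included, plus a listing. SAP section 7, which lists changes from the protocol, does not mention this set.

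**The concern.** The exclusion sentence is what a programmer would turn into a flag. In its usual sense, not satisfying either criterion means satisfying neither. On that reading, a DLT-free subject observed for 28 days after one of three VX-984 doses is not excluded, nor is one fully dosed but lost on Day 10. Both fail the inclusion sentence just above.

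The committee sentence gives no criteria and is not limited to subjects without a DLT. The missing Lead-in wording could drop a subject whose DLT occurred before Cycle 1.

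At stake is whether the DLT rates reported for the primary endpoint follow the protocol's definition. Cohorts hold 3 to 6 subjects (Protocol 8.1.2.1.2) and 6 treated subjects can be enough at the declared dose (Protocol 8.1.2.1.5), so one subject changes a rate noticeably.

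**Working it through.** There is no plan figure to reproduce. Protocol 12.1 states that Part A has no power calculation, and the documents give neither DLT counts nor numerical BLRM priors. The check is therefore a comparison of rules, followed by proportions on assumed counts.

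**Step 1. Subjects without a DLT: inclusion against exclusion.**

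| Exposure met | Observed through Cycle 1 | Inclusion sentence | Exclusion read as *meets neither* | Exclusion read as *fails any one* |
|---|---|---|---|---|
| yes | yes | in | kept | kept |
| yes | no | out | kept | removed |
| no | yes | out | kept | removed |
| no | no | out | removed | removed |

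The first reading contradicts the inclusion sentence in 2 of 4 rows, the second in none.

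**Step 2. Replaced subjects.** Protocol 9.6 confines Part A replacement to withdrawals for reasons other than DLT, before the Cycle 1 Day 28 assessment, without minimum exposure. Protocol 8.1.2.1.8 gives dose decisions to the Investigators and sponsor, and Protocol 12.3.7.2 marks IDMC analysis as not applicable. No Safety Monitoring Committee appears. The SAP sentence repeats none of the limits in 9.6.

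**Step 3. Lead-in DLTs.** SAP section 9 starts Treatment Day 1 with the first Cycle 1 dose and places the first Lead-in dose at Day -14, so a Lead-in DLT falls before Cycle 1. A subject with such a DLT who never starts Cycle 1 has no Cycle 1 DLT, no PLD exposure and no Cycle 1 observation. SAP 8.2 excludes that subject on either reading of the exclusion sentence. Protocol 12.2 includes the subject, and the SAP 15.1 table is meant to count the event.

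**Step 4. Size, on assumed counts.** The crude rate is r/n, with r subjects with a DLT among n in the set.

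- One under-exposed DLT-free subject kept: 2/6 = 33.3% becomes 2/7 = 28.6%.
- One subject with a DLT removed, by replacement or through the Lead-in gap: 2/6 = 33.3% becomes 1/5 = 20.0%.
- One DLT-free subject removed: 2/6 = 33.3% becomes 2/5 = 40.0%.
- If a share q of the set is wrongly kept with no DLTs, a rate p appears as p(1 − q). With p = 40%, q = 10% gives 36% and q = 20% gives 32%.

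Whether one extra subject crosses the limit depends on how 33.3% is read. Taken as 1/3, 2/5 = 40.0% exceeds it and 2/6 does not. Taken literally as 0.333, 2/6 = 0.3333 exceeds it and 2/7 = 0.286 does not. Two extra subjects (2/5 to 2/7) cross it on both readings.

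**The case against.** The strongest reply is that the inclusion sentence defines the set and an exclusion clause cannot bring anyone in. The clause can also be read as failing either one, which agrees with the inclusion sentence throughout. A reader might infer that the denominator of the primary endpoint is wrong. The documents do not show that: a programmer who follows the first sentence obtains the protocol's rule for DLT-free subjects. What stands is that one section supports two different programs.

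A reader might also infer that the MTD is biased upward. That is not supported either. Under Protocol 12.3.3 the MTD is estimated from the BLRM posterior with overdose control. Dose decisions are made by consensus (Protocol 8.1.2.1.8) using the protocol's own evaluability rules, not SAP 8.2. SAP 15.1 tests no proportion against 33.3%. Part B was dropped (SAP section 7), so no expansion dose depends on the table.

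On replacement, the unnamed committee may be the sponsor and Investigator group, and if it follows Protocol 9.6 it removes only subjects who are already non-evaluable. Judgement is not new: Protocol 12.2 already asks whether subjects "are considered by both the sponsor and Investigators to have enough safety data to conclude that a DLT did not occur". But that judgement concerns DLT-free subjects only, and the SAP neither identifies the committee nor cites 9.6. The protocol's limit also has a gap. Protocol 8.1.2.1.7 says "Subjects who do not fulfill at least 1 of the 2 above criteria will not be evaluable for dose escalation decisions and will be replaced", and its DLT criterion names only Cycle 1, whereas Protocol 8.1.2.1.2 and 12.2 also count the Lead-in Period.

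On the Lead-in wording, SAP 15.1 suggests that the authors meant to include it. SAP 8.2 does not say so.

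Safeguards exist: a data review meeting before lock (SAP 6.1) and a listing of excluded subjects with reasons (SAP 10.2). The listing shows who was removed, not who was wrongly kept.

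**Conclusion.** The point holds as an inconsistency in the definition of the set used for a primary endpoint. SAP 8.2 conflicts with itself for subjects who meet exactly one criterion. It also departs from Protocol 12.2, undeclared, on replaced subjects and Lead-in DLTs. The exposure is limited to the reported DLT rates; the in-trial BLRM dose decisions are untouched.

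In a set of about six, one subject moves the crude rate by roughly 5 to 13 percentage points (33.3% to 28.6%, 40.0% or 20.0%). This rests on assumed counts, on someone programming from the exclusion sentences, and on at least one such subject existing. The documents do not say whether any did.

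**What to change.** Amend SAP 8.2 and section 7:

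1. State that subjects without a DLT are excluded if they fail one or both of the two criteria.
2. Delete the committee sentence, or limit it to subjects without a DLT who are replaced under Protocol 9.6.
3. Restore the protocol's DLT limb, "or have had a DLT during Cycle 1 (including the Lead-in Period"), and use the same phrase in the exclusion sentence, so that a subject with a Lead-in DLT is not treated as DLT-free.
4. List any departure from Protocol 12.2 that remains in SAP section 7.

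The cost is a few sentences before database lock. No new data or analyses are needed, and the edit brings the set back to the protocol's rule.
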